Using fMRI and sEMG to Evaluate the Effects and Mechanism on Abdominal Acupuncture Combined With Upper Limb Rehabilitation Training on Brain Plasticity of Hemiplegic Patients With Stroke

Head of Clinical Research Unit: Guangdong Provincial Hospital of Chinese Medicine

Director of Clinical Research: [name]

Clinical Research Participating Unit: Guangdong Provincial Hospital of Chinese Medicine, Chinese University of Hong Kong.

Reporting Unit: Guangdong Provincial Hospital of Chinese Medicine

Research Director: [name]

Statistical Analysis Plan

Statistical analysis of our research will use SPSS 18.0 and MATLAB statistical software. The measurement data adopt T-Test, counting data use repeated measurement variance analysis and X2 test. And the image analysis adopt SPM8 software.

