3.1 Hemiplegic patients with first onset stroke were treated with abdominal acupuncture combined with upper limb rehabilitation training to observe the recovery of upper limb motor function, the muscles synergy monitored by sEMG, local brain area activation by fMRI and the integrity of pyramidal tract of cerebral white matter.

3.2 To analyze the changes of upper limb motor function the relationship between the changes and sEMG or brain fMRI

3.3 to explore the possible mechanism of abdominal acupuncture combined with upper limb rehabilitation training on brain plasticity of upper limb motor function recovery in hemiplegic patients with stroke.

4. Reporting Units and Research Units

Reporting unit: Rehabilitation Department of Guangdong Provincial Hospital of Chinese Medicine

Address: [name]

Research Director: [name] e-mail:[contact]

Clinical Auditor: [name] e-mail:[contact]

Head of Clinical Research Unit: Rehabilitation Department of Guangdong Provincial Hospital of Chinese Medicine

Address: [name]

Research Director: [name] e-mail:[contact]

Participating Units:

Rehabilitation Department of Guangdong Provincial Hospital of Chinese Medicine

Director: [name]

Chinese University of Hong Kong

Director: [name]

5. Research Design

5.1 Case selection: 66 patients diagnosed with initial stroke by CT/MRI and hospitalized in rehabilitation department of our hospital who meet the inclusion criteria will be included.

5.2 Random method: Patients met the inclusion criteria will be randomized into 3 groups by MATLAB stratified randomization software:

Treatment group A: abdominal acupuncture +upper limb rehabilitation training, 22 cases;

Treatment group B: Sham abdominal acupuncture +upper limb rehabilitation training, 22 cases;

Control group : upper limb rehabilitation training only , 22 cases.

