Sample size calculation: Using the SAMPSIZEPWR function calculation of MATLAB software Statistic Toolbox (Statistics Toolbox) to calculate, it is assumed that Fugl-meyer assessment (FMA) is the outcome index, and the FMA before rehabilitation training is also assumed to be 30 ± 10 (average \pm Standard deviation), the FMA after rehabilitation training is 37 (average). The amount of effect between groups is ~ 0.7 . If 0.8 of the statistical verification force is required, the sample size is 19 cases calculated by T-Test. Taking some uncontrollable factors that may causing dropping off into consideration, each group increases 3 cases with a 15% fall rate. Each group will include 22 cases.

5.3 Inclusion Criteria:

- ① First onset stroke, Left hemiplegia, Right-handed, and diagnosed by brain CT or MRI;
- ② Age 35 to 75 years old;
- ③ Course of disease 0.5 to 3 months with stable vital signs;
- ④ No cognitive impairment. Can understand and execute commands. MMSE score more than 7 points. ;
- ⑤ Can control the sitting balance. Brunnstrom stage of hemiplegic upper limb and hand is IV or V , Fugl-Meyer Motor Assessment score of upper limb 20-50 point;
- ⑥ Agree to sign the informed consent;
- ⑦ Unilateral neglect.

5.4 Exclusion Criteria:

- ① Recurrent stroke, subarachnoid hemorrhage, brain tumors patients;
- ② Contraindication to undergo a 3T MR imaging;
- ③ Claustrophobia;
- ④ Have severe heart, hepatic or renal failure;
- ⑤ Don' t cooperate with the treatment;
- ⑥ Have participated in other clinical trails recently.

5.5 Treatment Method:

Treatment group A: abdominal acupuncture +upper limb rehabilitation training;

Treatment group B: Sham abdominal acupuncture +upper limb rehabilitation training;

Control group : upper limb rehabilitation training only .

All the treatments above last for 30mins a time, once a day, five times a week, totally 4 weeks.

Upper limb Rehabilitation Training programme is based on the recommendations of the American AHA-ASA-2016-Stroke Rehabilitation Guideline , including instrumental activities of daily life training and upper limb operation therapy.

A: Instrumental activities of daily life training:

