Extend elbow (side): Subject attempts to reach across the table by extending the elbow (to the side).Extend elbow (to the side), with weight: Subject attempts to push the sandbag against outer wrist joint across the table by extending the elbow.Extend elbow (to the side), with weight: Subject attempts to push the sandbag against outer wrist joint across the table by extending the elbow. Hand to box (front): Subject attempts to place hand on the box.Pick up paper clip (front): Subject attempts to pick up paper clip by using a pincer grasp.Stack 3 checkers and flip 3 cards.Turning the key in the lock,fold towel,pick up the basket by grasping the handle and place it on the beside

table. Treatment Duration: 45 minutes a session, once a day, 5 times a week for 4 weeks.

B: Upper limb operation therapy:

According to the patient's specific situation, take the routine operation treatment. It includes the training of shoulder blades loosening, the active assistant and active training of the side upper limb, the joint activity training of the upper limb, the upper extremity training, and the grasping and opening of the side finger. Mainly with the side training, but also included a small number of contralateral auxiliary side training. Treatment time: 30 minutes/times, 1 times/day, 5 days/week, total 4 weeks.

5.6 Evaluation Method:

(1) Screening Assessment

Simple intelligent mental state scale (MMSE), and Brunnstrom upper limb movement staging will be evaluated once when included.

(2) Primary Outcome Measure:

Functional magnetic resonance imaging (fMRI) and surface electromyography (sEMG) are the two primary outcome, which will be tested before and 4 weeks after treatment, twice totally.

(3) Secondary Outcome Measure:

Wolf Motor Function Test; Brunnstrom staging of upper limb movement; Fugl-Meyer Motor Assessment of upper limb; Modified Barthel Index.

Time Frame: Before treatment, 2 weeks and 4 weeks after treatment, 3 times totally.

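### The SAP assigns repeated-measures ANOVA to counting data and leaves the three-arm, three-visit scale scores with only an unspecified t-test

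*SAP*

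**What the plan says.** The SAP has one sentence on tests: "The measurement data adopt T-Test, counting data use repeated measurement variance analysis and X2 test". The only addition is "And the image analysis adopt SPM8 software". It does not list which outcomes are measurement data and which are counting data. It does not say whether the t-test is paired or two-sample, whether it uses raw scores or change, which arms and visits it compares, or how multiple tests are handled.

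The design that this sentence has to serve is in the Protocol:

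- Section 5.2: patients "will be randomized into 3 groups by MATLAB stratified randomization software" (acupuncture plus training, sham plus training, training alone), 22 per arm.
- Section 5.6 (3), secondary outcomes: "Wolf Motor Function Test; Brunnstrom staging of upper limb movement; Fugl-Meyer Motor Assessment of upper limb; Modified Barthel Index", with "Time Frame: Before treatment, 2 weeks and 4 weeks after treatment, 3 times totally".
- Section 5.6 (2), primary outcomes: fMRI and sEMG "are the two primary outcome, which will be tested before and 4 weeks after treatment, twice totally".
- Section 5.2, sample size: FMA of 30 ± 10 before training and 37 after, an effect of about 0.7 described as between groups, and "If 0.8 of the statistical verification force is required, the sample size is 19 cases calculated by T-Test".

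**The concern.** Repeated-measures ANOVA is a method for continuous scores measured several times. The SAP attaches it to counting data, and the Protocol defines no count that is measured repeatedly. FMA, Wolf and Modified Barthel, which are measured repeatedly, are left with a t-test. A single t-test compares two means, whereas these scores form a layout of three arms by three visits.

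A two-sample t-test on change would be a valid comparison of one pair of arms. The SAP does not say that this is what is meant, so two readings are open and each has a cost:

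- **Before-after within each arm.** This does not compare arms. All three arms receive the rehabilitation training, so a significant gain in arm A cannot be separated from the gain due to training.
- **Pairwise between arms, unadjusted.** This does compare arms, but with several tests per scale and no control of the overall error rate.

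The three-visit problem concerns the secondary scales only. The primary sEMG measures, at two time points, presumably count as measurement data and inherit the same undefined t-test. The images have named software but no group contrast. The choice of comparison is therefore open until after the data are seen.

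**Working it through.** **1. Which t-test do the documents have in mind?** The only t-test with numbers is in the sample size paragraph of Protocol 5.2. Inputs: difference 37 − 30 = 7, SD 10, so d = 7/10 = 0.7; power 0.8. Alpha is not stated; 5% is assumed. Solving the noncentral-t power equation for n:

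| Form | Two-sided 5% | One-sided 5% |
|---|---|---|
| One-sample (before-after) | 18.03, so 19 | 14.07, so 15 |
| Two-sample, per arm | 33.02, so 34 | 25.94, so 26 |

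The Protocol's 19 is reproduced only by the two-sided one-sample form. This points to a before-after test, yet the same paragraph calls the effect between groups. The documents do not settle the form. (Whether the trial is large enough is a separate question and is not needed here.)

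**2. Within-arm reading.** Suppose acupuncture adds nothing and every arm gains the same 7 points. Take SD 10 at each visit (the Protocol gives it only before training) and an assumed between-visit correlation r. Then

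SD of change = 10 × √(2(1 − r)),

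and the power of the paired test in any one arm is the chance p that arm A is significant. Because the arms are independent, the chance that A is significant and the control is not is p(1 − p).

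| r | SD of change | p, n = 19 | p(1 − p), n = 19 | p, n = 22 |
|---|---|---|---|---|
| 0.5 | 10.0 | 82.3% | 14.6% | 87.9% |
| 0.6 | 8.9 | 89.7% | 9.2% | 93.8% |
| 0.7 | 7.7 | 96.1% | 3.8% | 98.1% |
| 0.8 | 6.3 | 99.5% | 0.5% | 99.9% |

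Example, r = 0.5 and n = 19: 0.823 × (1 − 0.823) = 0.146. At n = 22, p(1 − p) runs from 10.6% (r = 0.5) to 0.1% (r = 0.8).

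**3. Pairwise reading.** Simulation under no difference between arms, two-sided 5% t-tests, no adjustment:

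- Three pairs at one visit, n = 19: 12.2% chance of at least one false positive.
- Three pairs at both post-baseline visits, raw scores: 21.4% at r = 0.5 falling to 18.6% at r = 0.8 (n = 19); 21.5% to 18.5% at n = 22.
- Only two named week-4 contrasts (A vs sham, A vs control), n = 19: 9.0% unadjusted, 4.6% with Holm, 4.2% if done only after a significant overall three-arm F test.

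These figures measure multiplicity. They do not measure the mismatch between data type and test.

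**The case against.** The strongest reply is that the SAP never says which outcomes are counting data. Point and stage scales taken three times could be what is meant, with the t-test kept for instrument measurements taken twice. On that reading the scales do get a repeated-measures ANOVA. It fits the visit schedule, but the Protocol's sample size paragraph tells against it: it treats FMA by mean and SD and sizes it with a t-test, which is how one treats measurement data. Placing the scales there is still an inference, though the natural one.

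A second reply is that the labels were simply swapped, perhaps in translation. That is quite possible, but no other text corrects the sentence. Swapping them back would still leave the contrasts, the t-test's form, the multiplicity rule and the ordinal Brunnstrom stage undefined.

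Third, the three-visit outcomes are secondary, and for the two-time-point primary outcomes a two-sample t-test on change is valid for a given pair of arms. That is true and limits the scope. For sEMG and fMRI the fault is an unspecified comparison and not a wrong data type.

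Fourth, the size figures depend on the reading. The 82% at r = 0.5 is the Protocol's own design power restated, and the pattern of A significant with control not becomes rare at high correlation. Both remarks stand, so the figures are illustrations. The conclusion rests on the text.

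**Conclusion.** The concern holds, and the sentence should be corrected before analysis. As written, it gives repeated-measures ANOVA to a class of data with no repeated outcome. It leaves FMA, Wolf and Modified Barthel with no three-arm or arm-by-visit test. This is a stated rule that leads to the wrong analysis, and not only missing detail.

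The consequence depends on how the t-test is read: either a within-arm test that will usually be significant whether or not acupuncture works, or pairwise tests with an overall false-positive chance of about 12% at one visit and 18.5% to 21.5% over two. These sizes assume two-sided 5% tests and r between 0.5 and 0.8; the within-arm figures also assume SD 10 at each visit and the same 7-point gain in every arm. The finding that the sentence is wrong as written does not depend on them. It does depend on the scales being measurement data, which the SAP does not say but the sample size paragraph supports.

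**What to change.** Replace the sentence with a mapping from outcome to method:

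- **FMA, Wolf, Modified Barthel:** one repeated-measures or mixed model per scale with arm, visit and arm-by-visit. Name the week-4 contrasts A vs sham and A vs control. State the multiplicity rule: either Holm, or an overall three-arm test first.
- **sEMG and any scalar fMRI measure:** a three-arm linear model of the week-4 value adjusted for baseline, with the same contrasts and rule. For the SPM8 image analysis, state the group-by-time contrast.
- **Brunnstrom stage:** an ordinal model or a rank test between arms.
- **Chi-square or Fisher's exact test:** only for categorical data at a single time.
- **Within-arm before-after tests:** descriptive only.

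Other longitudinal models would also do. What matters is that the between-arm comparison and the multiplicity rule are fixed in advance.

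The change is to SAP wording only and needs no new data. The multiplicity rule costs some power. If A exceeds both comparators by 0.7 SD, power for A vs sham at 22 per arm falls from 63% unadjusted to 57% (Holm) or 55% (after the overall test). With 19 completers per arm it falls from 56% to 50% or 48%. These figures use t-tests with the variance pooled over the three arms, without baseline adjustment.

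### The SAP tests continuous outcomes by a t-test whose form, contrast and visit are unstated, and names no baseline covariate; baseline-adjusted ANCOVA would use data already collected, for a modest gain in precision.

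*SAP*

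**What the plan says.** The analysis section of the SAP is three sentences. After naming the software it states "The measurement data adopt T-Test", then "counting data use repeated measurement variance analysis and X2 test", then "And the image analysis adopt SPM8 software".

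Protocol 5.6(2) makes fMRI and sEMG the primary outcomes, "which will be tested before and 4 weeks after treatment, twice totally". Protocol 5.6(3) lists the secondary outcomes, "Wolf Motor Function Test; Brunnstrom staging of upper limb movement; Fugl-Meyer Motor Assessment of upper limb; Modified Barthel Index", with the schedule "Before treatment, 2 weeks and 4 weeks after treatment, 3 times totally". Every outcome therefore has a pre-treatment value.

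Protocol 5.2 allocates 22 patients to each of three arms by stratified randomisation, without naming the strata. Its sample-size paragraph works from Fugl-Meyer and concludes "the sample size is 19 cases calculated by T-Test". Neither document mentions a baseline covariate, ANCOVA or adjustment for strata.

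**The concern.** The SAP sentence on continuous data fits at least three analyses.

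- **Two-sample test of 4-week scores.** Valid, but it ignores the baseline measurement.
- **Two-sample test of change.** Valid, but it fixes the baseline slope at 1, which adds noise when r is low.
- **Before-after test within an arm.** This does not compare the randomised arms.

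If repeated-measures ANOVA was really meant for the scores, baseline enters only as one level of the time factor. With two visits (sEMG, or an fMRI summary) the arm-by-visit test is the change-score test. With three visits (Fugl-Meyer, Wolf, Barthel) it is a different test and does not isolate the 4-week difference.

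Two things are at stake: precision, in a trial with about 20 patients per arm, and the freedom to choose among these analyses after the data are seen.

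**Working it through.** **Inputs.** From the sample-size paragraph of Protocol 5.2: Fugl-Meyer SD 10, mean 30 before and 37 after, effect 0.7, power 0.8, 19 per arm before the dropout allowance. Assumed, because the documents do not give them: two-sided alpha 0.05 per contrast with no multiplicity adjustment; equal SDs at both visits; and r, shown over a range. Using 0.7 as a between-arm difference is also an assumption: the protocol labels it so, but its 7 points are a before-after rise.

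**Step 1. The plan's own figure.** With d = 7/10 = 0.7 and the noncentral t distribution:

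- One-sample or paired t-test: power 0.799 at n = 18 and 0.8225 at n = 19, so 19 is reproduced exactly.
- Two-sample t-test: 34 per arm needed (power 0.812); power at 19 per arm is 0.556.

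The form of the t-test therefore matters numerically, and the one worked example in the plan matches the before-after form.

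**Step 2. Variance of the A-minus-comparator difference, n per arm.**

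- Post-score: 2σ²/n, df 2n−2.
- Change: (2σ²/n) × 2(1−r), df 2n−2.
- ANCOVA: (2σ²/n) × (1−r²) × [1 + 1/(2n−4)], df 2n−3. The bracket is the cost of estimating the slope; at n = 19 it is 1 + 1/34 = 1.029.

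Before that cost, the ANCOVA variance relative to post-score is 1−r² = 0.91, 0.75, 0.51 at r = 0.3, 0.5, 0.7. Relative to change it is (1+r)/2 = 0.65, 0.75, 0.85. These ratios need no effect size, so they apply to any scalar outcome, including an sEMG measure once one is defined.

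**Step 3. Power for Fugl-Meyer, 19 per arm, two arms on every line.** Example at r = 0.5: noncentrality = 0.7 × √(19/2) / √(0.75 × 1.029) = 2.455, df 35, power 0.666.

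| r | Post-score | Change | ANCOVA | Gain over the better t-test (points) |
|---|---|---|---|---|
| 0.1 | 0.556 | 0.347 | 0.547 | −0.8 |
| 0.3 | 0.556 | 0.427 | 0.582 | 2.7 |
| 0.5 | 0.556 | 0.556 | 0.666 | 11.0 |
| 0.7 | 0.556 | 0.774 | 0.825 | 5.2 |
| 0.8 | 0.556 | 0.913 | 0.931 | 1.8 |

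Gains are from unrounded powers. If the error variance is pooled over all three arms for every method, they become −0.4, 3.1, 11.5, 5.5 and 2.0 points.

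**Step 4. 95% CI half-width in Fugl-Meyer points, 19 per arm, r = 0.3 / 0.5 / 0.7.** Post-score 6.58 throughout; change 7.79 / 6.58 / 5.10; ANCOVA 6.37 / 5.79 / 4.77.

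**Step 5. If repeated-measures ANOVA was meant for the three-visit scores.** Simulation, 10,000 trials per setting, equal correlation r between visits, effect in A only, 19 per arm, r = 0.3 / 0.5 / 0.7:

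- Two-arm arm-by-visit test, effect building linearly: 0.34 / 0.46 / 0.69.
- Two-arm arm-by-visit test, full effect by week 2: 0.45 / 0.58 / 0.81.
- ANCOVA at 4 weeks in the same runs, three arms fitted: about 0.60 / 0.68 / 0.84.

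The three-arm arm-by-visit test at r = 0.7 with full effect by week 2 has 0.84 at 19 per arm, level with ANCOVA. At 22 per arm it has 0.901 against 0.886, slightly ahead, although it is an omnibus test and so answers a different question.

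**Step 6. If within-arm tests were read against each other.** With a 7-point rise and SD of change 10 in both arms, and no true difference, the chance that A is significant and control is not is 0.8225 × (1 − 0.8225) = 0.146 at 19 per arm.

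**The case against.** The strongest reply is that leaving baseline out is a matter of efficiency. A between-arm t-test on post-scores or on change is valid under randomisation, and neither biases the estimate nor inflates type I error. That stands. A reader might infer that the planned t-test is invalid; the documents do not support this.

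A reader might also infer, from the sample size matching a paired test, that the trial will compare arms through before-after tests. The SAP states no such rule, and the protocol calls the effect one between groups. The 14.6% shows what the silence permits, not what is planned. A two-sample t-test would close that gap without ANCOVA.

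The size of the gain is also open to challenge. The 11-point figure is near the peak, at the r where the two t-tests tie. The Fugl-Meyer 20-50 entry window may lower r. The power figures concern a secondary outcome; for the primaries only the variance ratios apply. If repeated-measures ANOVA was meant, the advantage can vanish or slightly reverse. All of this stands and limits the point.

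What the objection does not remove is that no reading of the SAP fixes the test, contrast and visit, or uses the baseline values as a covariate.

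**Conclusion.** The point holds as a recommended improvement. The form, contrast and visit of the t-test are unstated, and no baseline covariate is named on either reading of the SAP. Against the better of the two valid t-tests, ANCOVA gains about 3, 11, 5 and 2 power points at r = 0.3, 0.5, 0.7 and 0.8, and about zero or slightly less at r = 0.1. That rests on an assumed between-arm difference of 0.7 SD on Fugl-Meyer, 19 per arm and two-sided 0.05. Against a three-visit repeated-measures ANOVA the gain depends on how the effect builds over time.

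It would go too far to conclude that ANCOVA rescues the planned sample size. At 19 per arm its power is 0.67 at r = 0.5 and passes 0.80 only at higher r, which the documents do not give. The sample-size calculation and multiplicity are separate matters. Maps analysed in SPM8 and the ordinal Brunnstrom stage are outside this point.

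**What to change.** For Fugl-Meyer, Wolf, Barthel and any scalar sEMG or fMRI summary once defined, replace the t-test sentence with:

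- ANCOVA of the 4-week value on arm, the same outcome's baseline value and the randomisation strata, fitted to all three arms.
- Adjusted A-B and A-control differences with 95% CIs.
- As an option for the three-visit scores, a repeated-measures model of the 2- and 4-week values with arm, visit, arm-by-visit and baseline as covariate, with the 4-week contrast named.
- A statement that no within-arm before-after test will be used to compare arms.

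**Cost.** No extra visit, patient or measurement, and the software already named suffices. The statistical price is one degree of freedom for the slope plus those for the strata. Three definitions must come first: the stratification factors, which Protocol 5.2 does not name; the Wolf score to be analysed, which 5.6(3) does not specify; and a scalar sEMG measure, since Protocol 3.1 says only "the muscles synergy monitored by sEMG".
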